Relevance to the VA Patient Care Mission. The number of OEF/OIF Veterans seeking care and rehabilitation services within the VA Health Care System is increasing rapidly. As such, the VA is faced with an increasing demand to provide evidence-based, treatment for Veterans. Sleep-wake disturbances with secondary impairments in functional outcome measures, cognitive function and increased chronic pain can adversely affect a Veteran's ability to reintegrate into civilian life, return to duty, succeed in competitive employment, or function independently. Failure to provide appropriate interventions and rehabilitation can also result in an increased need for health care services and VA benefits in the future. The knowledge gained from the current application, concerning the interacting relationship between cognitive/emotional health, headache/chronic pain and sleep, may help the VA improve interventions and outcomes with returning Veterans from combat in Iraq, Afghanistan, or elsewhere. Indeed, the development of sleep-based therapies with the strong potential to improve rehabilitation that optimally address the complex and unique needs of combat Veterans is critical to the VA patient care mission.

Preliminary Studies:

We have conducted several studies that highlight the need for this project and inform experimental design. Our preliminary data has examined; 1) the prevalence of sleep disturbances in Veterans – a cohort which identifies a large, immediately available pool of subjects for recruitment for this study, and 2) the feasibility of the MBLT intervention in Veterans with sleep disturbances.

MIRB #3641 and 3636

Title: *Factors that affect response to treatment for obstructive sleep apnea and related sleep disorders*

Publications:

Balba NM*, **[name]***, Weymann KB, Opel RA, Duke JW, Oken BS, **[name]**, Heinricher MM, **[name]**. Increased sleep disturbances and pain in Veterans with comorbid TBI and PTSD. *Journal of Clinical Sleep Medicine*, 2018. *denotes equally contributing authors

[name], Opel RA, Papesh MA, Weymann KB, Chau AQ, Callahan ML, Storzbach D, **[name]**. Sleep disturbances in TBI: Associations with sensory sensitivity. *Journal of Clinical Sleep Medicine*, 2018.

Relevance:

This protocol recruited 670 Veterans across an ~3-year time frame from the VA Sleep Disorders Clinic, demonstrating our ability to access and recruit large numbers of Veterans with sleep problems.

MIRB #4085 and 4086

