Title: *Morning bright light to improve sleep quality in Veterans*

Publications:

Data collection ongoing.

Relevance:

This protocol has recruited 91 participants over 18 months, 60 of which underwent MBLT for 4 weeks. The primary purpose of this protocol was to assess feasibility outcomes, including recruitment rate, retention rate, and adherence to the light therapy. Of the participants with TBI, 88% of subjects remained adherent to light therapy for the full 4 weeks. Overall, 91% of subjects said they liked using the lightbox. We additionally found that MBLT improves self-reported sleep, mood, and quality of life in our pilot cohort, however, this study lacks a placebo device for comparison.

Research Design and Methods:

Veterans within the VA Portland Healthcare System (VAPORHCS) and non-Veterans will be recruited for participation in this study. This study will consist of at least 4 visits over the span of ~5-6 mo.

Study Overview and Timeline.

	Visit 1	Visit 2	At Home	Visit 3	Visit 4 Follow up
Time point:	Day 0	Week 2	Week 2-6	Week 6	Week 10
Informed consent	X				
Subject given actiwatch		X		X	
Conduct pain assessment		X		X	X
Subject given lightbox or sham		X			
Questionnaires		X		X	X
Daily use of intervention for 1 hour			X		
Total time	~120 min	~120 min	28 hours	~120 min	~120 min

- *Informed consent and HIPAA authorization.* Written and verbal informed consent will be obtained before all other Visit 1 activities and may take place on an earlier date if DocuSign is able to be used to facilitate the consent conversation.
 - In cases where DocuSign is not feasible, consent conversations will take place in office space available at the VAPORHCS Sleep Disorders Clinic (building 100-6C), in related outpatient clinical space, or in Research Service space approved for human subjects use

(building 101, rooms 432A, 430, 404), or in subjects' homes. Alternatively, consent may take place remotely via phone or video conferencing via mailed documents.

- Where DocuSign is feasible, study staff will initiate email of a DocuSign envelope providing subjects access to the consent and authorization forms ahead of the consent discussion. Subjects will then be guided through downloading the fully executed consent form.

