Video Conferencing. If the subject is comfortable and equipped, we may conduct visits using video conferencing, such as VA Video Connect or other VA approved methods (skype, facetime, google hangouts, etc.). A link to the video chat will be emailed participants via Azure RMS encrypted email. For VA Video Connect (VVC), this email is entered into the VCC platform and an email is automatically generated.

At home visits. In special circumstances study personnel may travel to the subject's homes in order to conduct the visit more comfortably. Equipment, data, and specimens will travel in between the home and the VA only.

Phone calls. In between visits subjects will be contacted up to 2 times per week as needed. They will be assessed for understanding and compliance and given the opportunity to asked questions. Questions will be asked about their sleep, pain, and quality of life metrics.

Emails. Communication via RMS Azure encrypted email may be established between the subject and study coordinator in order to allow subjects to freely ask any questions they may have.

Study Population:

Number of subjects. The target population will consist of n=100 subjects. In order to meet this enrollment target we anticipate that up to 400 individuals may need to be recruited (consented) and screened.

Eligibility Criteria. Only Veterans and non-Veterans who are physically and mentally able to provide written and verbal informed consent and have a medical record-confirmed or physician confirmed diagnosis of TBI, will be included in this study. Additional criteria are as follows:

- 1) Current self-reported sleep-wake disturbances (defined by clinically abnormal Insomnia Severity Index and/or Functional Outcomes of Sleep scores)
- 2) Moderate to severe pain (defined as a score of ≥ 4 on an 11-point scale⁹⁰) persisting for longer than 6 months
- 3) Do not have a diagnosis for dementia
- 4) Are not currently using a lightbox or negative ion generator
- 5) Are not night-shift workers
- 6) Are English speaking with phone access
- 7) Are 18 years of age or older
- 8) Do not have macular degeneration or bipolar disorder (both are relative contraindications to regular bright light exposure)
- 9) No suicidal ideation
- 10) No cancer diagnosis in the past 6 months
- 11) At least 6-12 months of being surgery free
- 12) No evidence of drug and alcohol dependency (defined by the substance abuse and dependency scale).
- 13) Are currently living within the United States.

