and 1.0, after including a sham control group with postulated, one-treatment per arm sample sizes of 20-70, with a mean sample size of 47 and median of 50 post drop-out. This is consistent with prior studies that examined efficacy of MBLT therapy within comparable populations (e.g., circadian rhythm sleep disorders, insomnia, depression, or dementia), showing Hedges' g effect sizes ranging from 0.20 to 0.95 in sample sizes ranging between $n = 26$ to 42.³¹ Therefore, we intend to recruit 50 subjects per group. This sample size should be sufficient to detect clinically meaningful shifts in our outcome variables at levels that are robust enough to be accurately modeled and statistically evaluated.

Subject Identification/Recruitment

Research subjects will be recruited through word of mouth and several other methods:

1. **Repositories:** Participants may be recruited from an existing data repository at VAPORHCS (VA MIRB #3636, PI: [name], n=670 participants or VA MIRB #4086, PI: [name], n=200), approximately 30% of whom report TBI. These individuals have all provided informed consent for their data to be kept in the data repository and have given their permission to be re-contacted for future research studies.
2. **Sleep Clinic:** Veterans may be recruited from the VAPORHCS Sleep Disorders Clinic, or other outpatient clinics at VAPORHCS that have referred participants to us. Veterans will be approached in person or called on the phone, evaluated for eligibility in this study, and if interested, invited to undergo verbal and written informed consent.
3. **Flyers:** Volunteers may be recruited by fliers posted within the VAPORHCS, OHSU, and in the community. In the Portland VA, these flyers will be posted in the building 104 elevator, in handout stands in various clinics, and other VA bulletin boards with approved space for research flyers. They will also be given to clinicians at outpatient clinics to give to interested subjects. Interested subjects who contact us will then be screened over the phone with our phone script. If the participant is eligible and interested after the phone screen, we will plan to meet in person at VAPORHCS to get written and verbal informed consent.

Informed Consent & HIPAA Authorization:

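### Only current lightbox use is excluded, so people already treated with bright light in the team's own pilot can be re-recruited into the sham-controlled trial

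*Protocol*

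**What the plan says.** Under Study Population, Eligibility Criteria, item 4 requires that participants "Are not currently using a lightbox or negative ion generator". The wording is in the present tense. No other item mentions past light therapy or earlier participation in the light pilot.

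Under Subject Identification/Recruitment, the first route is the repositories: "Participants may be recruited from an existing data repository at VAPORHCS". The two named are #3636 (n=670) and #4086 (n=200). About 30% of members report TBI, and all have agreed to be contacted again.

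Under Preliminary Studies, the bright light pilot is headed "MIRB #4085 and 4086", so #4086 appears both with the pilot and as a recruitment source. Of the pilot the Protocol says: "This protocol has recruited 91 participants over 18 months, 60 of which underwent MBLT for 4 weeks". Its publication status is "Data collection ongoing". People with TBI took part, but their number is not given. The Protocol also reports that "91% of subjects said they liked using the lightbox" and that "this study lacks a placebo device for comparison".

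Under Research Design and Methods, the comparator is an ion generator with its ion function disconnected, possibly fitted with a fan that suggests activity. Participants are debriefed on the placebo condition at Visit 4.

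**The concern.** The sham works only if those who receive it can believe in it. The disabled generator, the optional fan and the late debrief all serve that end. Someone who has already spent four weeks with a lightbox, in a study by the same team of light for sleep, has reason to believe that light is the treatment under test. If allotted the ion generator, that person may expect less; if allotted the lightbox, more.

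All three aims rest wholly or partly on self-report, and quality of life rests on it alone, so expectation can move the outcomes directly. Randomisation does not remove this. Balancing prior users between the arms does not cancel the effect, because the same belief can act in opposite directions in the two arms.

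There is also a link to the sample size. The Power analysis draws on data from #4085 and postulates a placebo effect half as large as the MBLT effect seen in the pilot. People who have already had the active treatment are those in whom that postulate is least safe.

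**Working it through.** **The plan's own figure.** The Protocol gives no share of previously treated participants, so there is none to reproduce. The nearest stated figure is 50 per group. Alpha, power and dropout are not given as numbers; I assume two-sided 0.05 and 80% power.

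- n per arm = 2 × (1.960 + 0.842)² / d². For d = 0.5 this is 63, and for d = 1.0 it is 16. That is broadly in line with the stated 20 to 70 per arm for effects mostly between 0.5 and 1.0.
- Difference detectable with 50 per arm = 2.802 × √(2/50) = 0.56 SD.

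**Inputs from the Protocol.** Pilot recruits to date 91, of whom 60 had light (Preliminary Studies). Repository sizes 670 and 200, with about 30% reporting TBI (Subject Identification/Recruitment). Target 100, with up to 400 consented and screened (Study Population).

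**Share of the trial that could be prior users.** Each line needs an assumption that the Protocol does not supply.

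- Screening yield of 100 in 400 applied to 18 people: 18 × 100/400 = 4.5, or 4.5% of 100.
- Enrolment proportional to the two repositories, with all participants drawn from them: 60/(670 + 200) = 6.9%, about 7 of 100.
- Every light-treated pilot participant with TBI enrols, with the 30% applied to the 60: 60 × 0.30 = 18, or 18%.
- The treated fraction 60/91 holds for all 200 in #4086, and all of those with TBI enrol: 200 × 60/91 = 132; 132 × 0.30 = 40, or about 40%.

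**Bias.** Assume that prior users form the same share of each arm, and that each prior user on sham loses a placebo response of 0.5 SD. The sham mean then falls by share × 0.5. The last column is the two-sided rejection rate when light has no specific effect, with 50 per arm and a normal approximation: Φ(δ/√(2/50) − 1.96) + Φ(−δ/√(2/50) − 1.96), where δ is the bias.

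| Share | Bias δ (SD) | Rejection rate under the null |
|---|---|---|
| 7% | 0.07 × 0.5 = 0.035 | 5.4% |
| 18% | 0.18 × 0.5 = 0.09 | 7.4% |
| 40% | 0.40 × 0.5 = 0.20 | 17.0% |

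At the 4.5% share the bias is 0.045 × 0.5 = 0.02 SD. Against a net effect of 0.5 SD, the lower end of the range in the Power analysis, 0.09 SD is 18%. Raised expectation in the light arm is not included and would add to these figures.

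**The case against.** The case for giving this little weight has several parts.

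- **The share.** A reader might infer that at most 18% of the sample could be prior users. The documents do not support 18% as a ceiling or as an expected value. The 30% is a repository-wide figure for reported TBI, whereas entry needs a confirmed diagnosis, long-standing pain and abnormal sleep scores, so the true share may be well below 18%. It could also be higher, because the pilot is still collecting data and #4086 is listed at 200. This objection stands, and the share is therefore given as scenarios.
- **Knowledge of allocation.** A reader might infer that these people know which device is inert. Nothing says so. Having used a lightbox does not reveal that the ion generator is disabled. What stands is the weaker statement that they have reason to think light is the treatment under test.
- **Direction.** A former pilot participant who still has poor sleep and pain, and no longer uses a lightbox, may be someone whom light did not help. That could lower expectation in the light arm and shrink the difference. The reported liking for the lightbox is for the pilot overall, not for this group. Inflation is likely, not established.
- **The 0.5 SD.** The Power analysis postulates only a ratio of one half. It does not state a placebo response in SD units; the 0.5 is my assumption.
- **The pilot link.** The Power analysis cites #4085 and recruitment cites #4086. No passage says how many of the 60 are in #4086, and 31 of the 91 (91 − 60) are not reported as having had light. The overlap is probable but uncounted.
- **Specificity.** The two devices differ visibly for everyone, so expectation differences are not confined to prior users.

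None of this touches the text itself: past treatment is not excluded, and a repository tied to the light pilot is a named source. Applying the same criteria to everyone, which the Protocol offers as protection against recruitment bias, does not address prior exposure. Nor would an unseen statistical analysis plan, because eligibility is fixed here.

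**Conclusion.** The gap is real: the Protocol allows people whom this team has already treated with MBLT, without a sham, to be randomised in a trial that depends on a believable sham and largely on self-report. Its size cannot be settled from the Protocol. The bias is about 0.035 to 0.20 SD over shares of 7% to 40%, and about 0.02 SD at the 4.5% screening-yield share. All of these rest on the assumed 0.5 SD loss of placebo response and on equal shares in the two arms. Only the upper scenario would be serious on its own; at 7% the effect on error rates is slight. The documents do not support saying that prior users know which device is inert, that 18% is a limit, or that the difference must be inflated. The point merits a change because the threat is specific to the sham and cheap to remove, not because the trial is shown to be biased by a known amount.

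**What to change.** Extend criterion 4 so that it also excludes anyone who received MBLT under MIRB #4085/4086. If enrolment is already advanced, identify prior users from the pilot records and repeat the main comparison without them; that repeat analysis can be specified in the statistical analysis plan.

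The cost is a modestly smaller repository pool. Candidates with TBI number about (670 + 200) × 0.30 = 261. Removing 18 of them loses 18/261 = 7%; in the largest scenario, about 40/261 = 15%. The clinic, flyer, word-of-mouth and non-Veteran routes are unaffected.

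The change does not remove the expectation difference that two visibly different devices can cause in all participants.

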This proposal aims to apply a sleep intervention to improve chronic pain in Veterans with TBI. We propose to use morning bright light therapy (MBLT), a readily deployable, cost-effective, non-pharmacologic, and home-based sleep intervention, to improve sleep-wake disturbances and therefore ameliorate chronic pain and improve quality of life in Veterans with TBI. There is substantial scientific precedent for MBLT to be effective in improving sleep quality, as outlined by a recent meta-analysis of 53 MBLT-based studies.³¹ Indeed, the potential of MBLT to improve sleep quality in Veterans with TBI remains unexplored, and yet, highly promising. Outcomes will be assessed pre- and post-intervention, and at a 3-month follow-up time point. *Our central hypothesis is that MBLT will improve sleep quality and ameliorate pain, resulting in improved quality of life in Veterans with TBI.*

Specific Aim 1: Determine the effect of MBLT on *sleep quality* in Veterans with TBI.

- Hypothesis: Self-reported sleep quality, and sleep efficiency using actigraphy, will improve following 4-weeks of MBLT compared to sham in Veterans with TBI.

Specific Aim 2: Determine the effect of MBLT on *pain* in Veterans with TBI.

- Hypothesis: Self-reported pain, and pain testing via pressure algometry, will improve following 4-weeks of MBLT compared to sham in Veterans with TBI.

Specific Aim 3: Determine the effect of MBLT on *quality of life* in Veterans with TBI.

- Hypothesis: Self-reported quality of life will improve following 4-weeks of MBLT compared to sham in Veterans with TBI.

Scientific Rationale and Significance:

Sleep-Wake Disturbances Following TBI. It is nearly universally accepted that one of the principal complicating factors associated with TBI is sleep-wake disturbances. The functional and economic impact of sleep disturbances is staggering¹⁸ and well-known to *directly impair quality of life*,¹¹ preclude independent functioning, reintegration into civilian life, return to duty or success in vocational endeavors.

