Our MBLT protocol is based off much of this previous work,³¹ including studies using MBLT to treat sleep-wake disturbances in patients with neurodegenerative conditions (e.g., dementia, Alzheimer's, Huntington's and Parkinson's disease),⁷⁸⁻⁸⁰ and fatigue in cancer patients⁸¹ healthy office workers,^{82,83} and civilians with TBI.⁸⁴ Specifically, Veterans will engage in 60 minutes of MBLT at 10,000 lux for 4-weeks, for which there is a large body of evidence.³¹

Innovation and Impact. The high prevalence, profound disability, and economic impact associated with combat derived TBI in Veterans is undeniable and underscored by TBI-related research being among the highest priorities within Veteran Affairs Office of Research and Development and specifically Rehabilitation Research & Development.^{45,85,86} The pathophysiology of TBI-related disability is multifaceted, complex, and creates an extremely complicated patient to treat, with poor sleep quality and chronic pain playing a central role. For this reason, there is substantial scientific precedence for rehabilitative strategies that target improved sleep quality to not only improve these quality of life metrics, but likely also improve the efficacy of ongoing symptom directed rehabilitation.^{22,87-89}

The primary product of the proposed study is empirically validating MBLT to be effective for improving sleep quality in Veterans with TBI, as well as ameliorating chronic pain and improving quality of life. In doing so, we will gain a better understanding of the impact that improved sleep has on these, and other, highly relevant functional outcomes in Veterans with TBI. Several factors set MBLT aside as a potentially extremely high-yield therapeutic option, such as it being rapidly deployable, cost-effective, non-pharmacologic, and home-based. Therefore, the proposed study is likely to have a significant effect on the quality and effectiveness of rehabilitative services offered to our Veterans.

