- *Actigraphy.* Subjects will be asked to wear an individually configured actigraphy watch (Phillips Respiration Actiwatch 2) for the entirety of the study. This actiwatch collects data related to subject's sleep-wake cycle, including activity (via a built-in accelerometer) and light exposure (via a built-in luxometer). Watches are user friendly, requiring no user input to operate, and batteries last for ~6 weeks. Subjects will be reminded to keep clothing from covering up the luxometer on the actiwatch as much as possible.
- *Study diary.* Subjects will be asked to fill out a study diary, with daily entries for the entirety of the study. They will record when they went to bed, when they woke up, when they used the lightbox, and days they went to work. At this point subjects will be educated on principles of good sleep hygiene, such that all subjects start at the same baseline with respect to their understanding of good sleep hygiene principles. Study diaries will be coded via subject's ID with no other identifiable information listed.
- *Pain testing.* Pressure-pain threshold and tolerance will be quantified using a pressure algometer (AlgoMed Computerized Pain Pressure Algometer), a validated device used both experimentally and clinically with the pressure stimulus delivered to the thumbnail/thenar region of the non-dominant hand. Threshold will be determined by the amount of pressure that the subject perceives as mildly painful. Tolerance will be determined by the amount of pressure that causes the subject to withdraw their hand. This test takes ~20 min to complete.
- *Pain testing.* Cold Pressor Test. The cold pressor test may be used at VAPORHCS and at visits that are conducted remotely. This test will consist of an ice bath that subject's are instructed to submerge

their non-dominant hand into. Threshold and Tolerance will be measured with a stop watch. Threshold will be determined by the amount of time that the subject perceives the temperature as mildly painful. Tolerance will be determined by the amount of time that causes the subject to withdraw their hand. This will be done during a single trial. The upper limit of allowing the hand in the icebath is 5 minutes.

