Our inclusion/exclusion criteria will not exclude any specific class of persons who might benefit from the proposed research. Every effort will be made to include women and minority groups in this study. All Volunteers meeting inclusion/exclusion criteria will be invited to participate in the study, regardless of gender or racial/ethnicity status. Women comprise 8.5% of the Veterans included in the established VAPORHCS Sleep Disorders Data Repository (MIRB #3636) and minorities 8.3%. The same inclusion/exclusion criteria are applied for all participants which ensures that there is no recruitment bias to confound the results.

Every effort will be made to recruit Veterans for the completion of this project. However, we will plan to recruit non-Veterans as necessary to ensure sufficient data to answer study questions. The Veteran population is disproportionately male and often burdened with significant health issues. Thus, the inclusion of non-Veteran recruitment will help ensure greater recruitment eligibility and enrich for the inclusion of more women and underrepresented minorities. While we will not specifically target active military personnel for recruitment, we will also include them when they reach out to project staff about participating.

Power analysis. From pilot data collected via MIRB #4085, as well as from literature regarding MBLT interventions, a power analysis was conducted in order to estimate the sample size needed to detect a statistically robust difference in the described primary outcome variables at an acceptable level of significance and power with a clinically meaningful level effect size. In order to account for the inclusion of the sham control, a placebo effect size was postulated at 50% of the observed MBLT effect with the same variance in outcomes as observed in the pilot cohort. This led to a postulated collection of effect sizes necessary to observe differences in the various outcomes between the MBLT and a sham control. Most fell between 0.5

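### The sample size is set for primary outcomes that the protocol never names, so the claim that 50 per group suffices cannot be tied to any test and fails for outcomes needing more than 50

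*Protocol*

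**What the plan says.** The Power analysis paragraph (Protocol, Study Population) states that the calculation was made to "detect a statistically robust difference in the described primary outcome variables at an acceptable level of significance and power". It gives no significance level, sidedness, power or drop-out rate. It takes the sham effect as half the observed light-therapy effect and reports a set of standardised differences, one per outcome ("Most fell between 0.5" and 1.0). The matching per-arm sizes run from 20 to 70, with mean 47 and median 50. The paragraph then adopts 50 per group and says this should be enough for clinically meaningful shifts in the outcome variables.

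The outcomes appear under Specific Aims/Purpose:

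- Aim 1: "Self-reported sleep quality, and sleep efficiency using actigraphy, will improve following 4-weeks of MBLT compared to sham".
- Aim 2: "Self-reported pain, and pain testing via pressure algometry, will improve following 4-weeks of MBLT compared to sham". The Visit 2 procedures show that algometry yields two readings: "Pressure-pain threshold and tolerance will be quantified using a pressure algometer".
- Aim 3: self-reported quality of life.

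None of these is called primary. The nearest wording is under Innovation and Impact: "The primary product of the proposed study is empirically validating MBLT to be effective for improving sleep quality in Veterans with TBI". That sentence goes on to add pain and quality of life, and it names no measure.

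**The concern.** The sizing sentence refers the reader to primary outcomes described elsewhere, and they are not there. This is more than missing detail. A primary endpoint is not normally left to a statistical analysis plan, and the protocol rests its adequacy claim on having one.

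Two things are at stake. First, the required sizes differ by a factor of 3.5 (70/20), so a single statement that 50 per group is enough cannot be true to the same degree for every outcome. Second, if the primary outcome were chosen after results by arm were known, the choice could follow the data and bias the trial's main conclusion. The protocol does nothing to prevent that.

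**Working it through.** **Inputs from the Power analysis paragraph.** Standardised differences mostly 0.5 to 1.0; per-arm sizes 20 to 70, mean 47, median 50; 50 per group chosen. **Assumed, because not stated:** two-sided 5% and 80% power per outcome. 90% power is also tried.

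**Step 1: can the stated sizes be reproduced?** For two equal arms, n per arm = 2(1.960 + 0.842)²/d² = 15.70/d².

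- d = 0.5: 15.70/0.25 = 62.8, so 63 (64 with the t distribution).
- d = 1.0: 15.70, so 16 (17 with the t distribution).
- With an assumed 10% drop-out: 64/0.9 = 71.1, so 72; 17/0.9 = 18.9, so 19.

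This is close to 20 to 70, so outcome-by-outcome sizing at about these settings is plausible. It is not a strict reproduction. One-sided 5% with 90% power gives 69 to 70 and 18, which fits about as well.

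**Step 2: power at 50 per arm for an outcome needing n per arm.** The noncentrality scales with the square root of the sample size, so

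power = Φ[(1.960 + 0.842)·√(50/n) − 1.960].

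| Size the outcome needs | Calculation | Power at 50 per arm |
|---|---|---|
| 20 | 2.802 × 1.581 − 1.960 = 2.470 | about 99% |
| 50 | 2.802 × 1.000 − 1.960 = 0.842 | 80% |
| 60 | 2.802 × 0.913 − 1.960 = 0.598 | about 72% |
| 70 | 2.802 × 0.845 − 1.960 = 0.408 | about 66% |

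If the sizes were calculated for 90% power, 1.282 replaces 0.842. An outcome needing 70 then has Φ(3.242 × 0.845 − 1.960) = Φ(0.780), about 78%, against an intended 90%. If the sizes include a drop-out allowance, the ratio 50/70 is unchanged as long as both figures are on the same basis.

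**Step 3: what the median implies.** With a median of 50, at least half of the outcome-specific sizes are 50 or more. The protocol does not say how many exceed 50, or which outcomes they are.

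**Step 4: does it matter which outcome is primary?** The section on light-therapy precedent cites effect sizes of 0.77 for sleep quality and 0.38 for sleep efficiency, the two halves of Aim 1. Taken as between-arm differences (an assumption; they come from a non-TBI civilian population and are not the protocol's planning values), power at 50 per arm is Φ(0.77 × 5 − 1.960) = Φ(1.89), about 97%, and Φ(0.38 × 5 − 1.960) = Φ(−0.06), about 48%. The same sample size is ample for one and poor for the other.

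**The case against.** The strongest reply is that the Aims already fix the comparison (light therapy against sham), the timing (after 4 weeks) and a short list of outcomes, and that these are plainly the outcomes the power section means. Each may be tested and reported on its own, which is what outcome-by-outcome sizing describes. Testing order and multiplicity rules may sit in a statistical analysis plan that is not shown. Much of this stands, and it rules out several stronger readings.

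- A reader might infer that, because Aims 1 and 2 each join outcomes with the word *and*, either the power or the error rate of the Aim must be wrong. The wording is a hypothesis, not a decision rule, and separate testing is a natural reading. Under that reading neither consequence follows. Aim 3 has only one outcome in any case.
- A reader might say that the stated significance level fails. None is stated.
- Joint power for a pair at an assumed 80% each is 0.8 × 0.8 = 64% if independent and about 71% at correlation 0.7. The chance of at least one false positive in six unadjusted tests is 1 − 0.95⁶, about 26%, if independent and about 21% at correlation 0.5. These figures are illustrative only. They assume equal power for outcomes whose required sizes differ widely, or pool three Aims into a family the protocol does not propose.
- A reader might take the primary-product wording to make sleep the primary outcome. The same sentence also covers pain and quality of life.

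The reply does not repair the sizing sentence. A list of outcomes with equal standing does not identify a primary one, and separate testing still leaves those needing more than 50 per arm below their intended power.

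**Conclusion.** The point holds in a limited form. The protocol sizes the trial for primary outcomes it does not designate, so 50 per group corresponds to no identifiable test. The general statement that 50 is enough fails for any outcome whose own calculated size is above 50. At the top of the protocol's range, power is about 66% rather than 80%, or about 78% rather than 90%, depending on which target was used. Both figures assume a two-sided 5% level.

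How many outcomes are affected, and whether the intended primary is one of them, cannot be derived from the document. The absence of a multiplicity rule is not part of this conclusion.

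**What to change.** Before any outcome is examined by arm:

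1. In Specific Aims/Purpose and in Power analysis, name one primary outcome measure and one time point: the end of the 4-week intervention, which the study timeline places at Visit 3. A specific self-reported sleep measure would fit Aim 1 and the primary-product sentence, but the choice is the sponsor's.
2. Label the other outcomes secondary, with pressure threshold and tolerance listed separately.
3. Replace the reference to described primary outcomes with the named one. State its alpha and sidedness, its assumed effect size, its own per-arm size from the 20 to 70 range, and its power at 50 per arm.
4. Restrict the claim of adequacy to outcomes whose calculated size is 50 or less.
5. If an Aim is meant to require both of its outcomes, say so and restate the power on that basis.

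The change is mostly wording. Its price is that fewer outcomes can be claimed as confirmatory and the sample size will look less favourable than it does now. If the named outcome needs more than 50 per arm, or if both outcomes of an Aim are required, the sponsor must either accept the lower power openly or revisit the number of subjects.
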